5.1.3 Primary Endpoints

The primary effectiveness endpoint is the surgical success rate defined as the procedure not going into conversion. Conversion is defined as the switch from a robotic-assisted approach using the Hugo system to a robotic-assisted approach utilizing an FDA cleared robotic-assisted device, laparoscopic or open surgery.

The primary safety endpoint is the rate of subjects with complications meeting Grade III criteria or higher per the Clavien-Dindo Classification system¹ from the first incision through 30 days post-procedure.

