12.1 Adverse Events

All Adverse Events (AEs) will be collected, starting from the time the informed consent form is signed through 30 days (+7) after the day of the procedure regardless of their severity or relationship to the Hugo™ RAS or study procedures. After 30 days, AEs will be assessed by the surgeon and those AEs deemed attributable to the underlying surgical indication, procedure or surgical device will be reported. All deaths will be collected via AE regardless of relatedness. Reporting of these events to Medtronic will occur on an AE Form, including event description, date of AE, treatment, resolution, assessment of both the seriousness of the AE and the relatedness to the system components. Each AE must be recorded on a separate AE eCRF.

AE definitions used in this study are based on ISO 14155:2020 (Clinical Investigation of Medical Devices for Human Subjects -- Good Clinical Practice). Documented pre-existing conditions are not considered AEs unless the nature or severity of the condition has worsened. See **Section 14.1** for details regarding AE analyses in each study analysis set. In addition, AEs impacting users or other persons (non-subject AEs) will be collected on a non-subject AE CRF.

Any unresolved procedural or device-related events that are still ongoing past study exit will be monitored by the physician per their institutional standard-of-care.

Unavoidable adverse events (UAE) (those that are inherent to the procedure and are expected to occur in all subjects for an expected duration) listed in **Table 9** will not be captured or reported unless the adverse event worsens or persists outside the stated timeframe post procedure. **Section 11.1** includes a list of several, but not an all-encompassing anticipated adverse events.

All deaths, serious adverse events related to the Hugo™ RAS System and/or study procedures and Clavien-Dindo Grade III and IV complications will be adjudicated by an independent CEC.

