Complication	
Complications will be defined according to the Clavien-Dindo classification system.¹
 
Grade I: Any deviation from the normal postoperative course without the need for pharmacological treatment or surgical, endoscopic, and radiological interventions. Allowed therapeutic regimens are: drugs as antiemetics, antipyretics, analgetics, diuretics, electrolytes, and physiotherapy. This grade also includes wound infections opened at the bedside.
 
Grade II: Requiring pharmacological treatment with drugs other than such allowed for grade I complications. Blood transfusions and total parenteral nutrition are also included.
 
Grade III: Requiring surgical, endoscopic, or radiological intervention
 
Grade IIIa: Intervention not under general anesthesia
 
Grade IIIb: Intervention under general anesthesia
 
Grade IV: Life-threatening complication (including CNS complications)* requiring IC/ICU management
 
Grade IVa: Single organ dysfunction (including dialysis)
 
Grade IVb: Multiorgan dysfunction
 
Grade V: Death of a patient

Medtronic Business Restricted

This document is electronically controlled

CONFIDENTIAL 056-F275 Rev E Clinical Investigation Plan Template

	
NOTE 1: If the patient suffers from a complication at the time of discharge (see examples in Appendix 18.1), the suffix "d" (for "disability") is added to the respective grade of complication. This label indicates the need for a follow-up to fully evaluate the complication.
 
NOTE 2: *Brain hemorrhage, ischemic stroke, subarachnoidal bleeding, but excluding transient ischemic attacks. CNS, central nervous system; IC, intermediate care; ICU, intensive care unit.

Other	

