12.6.1 Death Classification and Reporting

Sufficient information will be required in order to properly classify the subject's death. The Investigator shall classify each subject death per the following definitions:

- Cardiac Death: A death directly related to the electrical or mechanical dysfunction of the heart.
 - Sudden Cardiac Death: Natural death due to cardiac causes, indicated by abrupt loss of consciousness within one hour of the onset of acute symptoms; preexisting heart disease may have been known to be present, but the time and mode of death are unexpected. If time of onset cannot be determined, SCD will alternatively be defined as any unexpected cardiac death occurring out of the hospital or in the emergency room as dead on arrival.
 - Non-sudden Cardiac Death: All cardiac deaths that are not classified as sudden deaths, including all cardiac deaths of hospitalized subjects on inotropic support.
- Non-cardiac Death: A death not classified as a cardiac death.
- Unknown Cardiac Classification: Unknown death classification is intended for use only when there is insufficient or inadequate information to classify the death

The CEC will review all deaths and provide a final adjudication of the relatedness of death.

Regulatory reporting of Subject Deaths will be completed according to local regulatory requirements.

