30 days)	Prostatectomy	25.6%	The mean effect size was 0.062 with a 95% confidence interval of 0.005 to 0.469. The 95% prediction interval was not able to be obtained due to a lack of data, as there were only two cohorts as part of this meta-analysis. The highest literature-reported reoperation rate within 30 days was 0.156, applying a 10% absolute margin to this gives 0.256. Thus, a performance goal of 25.6% was set and deemed to be clinically appropriate.
	Cystectomy	25.6%	There was no literature found, therefore the prostatectomy performance goal was leveraged to assign a performance goal of 25.6%.
Mortality rate (through 30 days)	Nephrectomy	24.3%	Limited to two cohorts from one study, the performance goal is derived based on the individual cohort upper limits of 0.143. A value of 0.243 provides 10% margin on the upper limit, while remaining clinically appropriate.
	Prostatectomy	21%	Limited to one cohort, the performance goal is derived based on the individual cohort upper limit of 0.110. A value of 0.210 provides 10% margin on the upper limit, while remaining clinically appropriate.
	Cystectomy	35.1%	This analysis was based on 6 cohorts. As there was no variance between cohorts, the performance goal is derived based on the individual cohort upper limits of 0.040 to 0.251. A value of 0.351 provides 10% margin on the upper limit, while remaining clinically appropriate.
Rate of device deficiencies	Nephrectomy	20%	Device specific deficiencies were not reported in the literature. Recognizing that device deficiencies include those of preference and not all will impact the safety or performance of the device, a clinically appropriate performance goal of 20% has been selected.
	Prostatectomy	20%	Device specific deficiencies were not reported in the literature. Recognizing that device deficiencies include those of preference and not all will impact the safety or performance of the device, a clinically appropriate performance goal of 20% has been selected.

Medtronic Business Restricted

This document is electronically controlled

CONFIDENTIAL 056-F275 Rev E Clinical Investigation Plan Template

Medtronic Expand URO Clinical Investigation Plan

MDT19051EINURO

Version 9.0

Page 77 of 111

Medtronic

Endpoint	Procedure Type	PG	Rationale

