16.10.2.1 Study-wide Termination or Suspension

Possible reasons for considering study-wide suspension or termination of the study include but are not limited to:

- AEs associated with the system or product under investigation which might endanger the safety or welfare of the subject
- Observed/suspected performance different from the product's design intent
- Decision by Medtronic or RA (where the study is operating under RA)
- Technical issues during the manufacturing process

Clavien-Dindo Grade IV complications will be continuously monitored by the sponsor for the safety and well-being of the subjects. Events reported as Clavien-Dindo Grade IV will be assessed by the Investigator and the sponsor as well as sent for adjudication by the independent CEC upon the sponsor's awareness date for the reported event.

Safety thresholds for Grade IV complication rates for the three study procedures are noted below:

- Cystectomy: 10%
- Nephrectomy: 8%
- Prostatectomy: 5%
- The above safety thresholds will be used by the sponsor to modify or stop the trial. The sponsor will review the Clavien-Dindo Grade IV complications for the first 30 subjects with 30-day data. A second review will be conducted for the second 30 subjects with 30-day data to ensure ongoing monitoring of subject safety.

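### The numeric modify-or-stop thresholds count Clavien-Dindo Grade IV only, so a complication recorded only as a death (Grade V) adds nothing to them

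*Protocol*

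**What the plan says.** Protocol Section 16.10.2.1 contains the only numeric stopping guidance in the available text. It introduces the limits with "Safety thresholds for Grade IV complication rates for the three study procedures are noted below" and lists 10% for cystectomy, 8% for nephrectomy and 5% for prostatectomy. On their use it says "The above safety thresholds will be used by the sponsor to modify or stop the trial". On timing it says "The sponsor will review the Clavien-Dindo Grade IV complications for the first 30 subjects with 30-day data", followed by a second review for the second 30 subjects. The sentences on continuous sponsor monitoring and on referral to the CEC also name Grade IV alone.

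Table 7 in Section 12.4 gives death its own grade: "Grade V: Death of a patient". Grade IV there is a life-threatening complication that needs intermediate or intensive care.

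Deaths are handled in other sections. Section 12.6 asks for a report as soon as possible, on a single adverse event record carrying the fatal outcome. Section 12.6.1 says "The CEC will review all deaths and provide a final adjudication of the relatedness of death". Section 16.10.2.1 itself opens with a non-exhaustive list of reasons for suspending or terminating the study. The SAP contains no stopping rule.

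**The concern.** The thresholds state in advance what level of serious harm should make the sponsor modify or stop the trial. As written, a subject who survives intensive care counts toward the limit, and a subject whose complication is recorded only as a death does not. The worse outcome gives the lower reading.

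Elsewhere the protocol includes death in words when it means to. The primary safety endpoint uses "complications meeting Grade III criteria or higher per the Clavien-Dindo Classification system", which takes in Grade V. The adjudication rule in Section 12.1 covers "All deaths, serious adverse events related to the Hugo™ RAS System and/or study procedures and Clavien-Dindo Grade III and IV complications": deaths are named separately there, so the phrase for Grades III and IV is not being relied on to cover them. Section 16.10.2.1 uses neither device.

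The case can arise in practice. Because Section 12.6 asks for one record per death, a complication that ends fatally need not leave a separate Grade IV entry.

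**Working it through.** The protocol gives no derivation for the 10%, 8% and 5% levels, so there is no plan figure to reproduce. The main result is textual; the arithmetic shows its size.

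**Step 1: what enters the numerator.** The rate for a procedure is (subjects with a Grade IV complication) / (subjects of that procedure under review). A complication graded V and nothing else adds 0 to the numerator. This holds for any number of subjects and any mix. A Grade IV event reported separately before the death would still count.

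**Step 2: cohort sizes at the first review.** Inputs are the 30 subjects in Section 16.10.2.1 and the caps of 31, 55 and 55 (total 141) in Section 14.7. I read the 30 as pooled over procedures, because two sets of 30 per procedure would need 60 subjects against those caps. If the first 30 follow the planned mix:

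- cystectomy: 30 × 31/141 = 6.6, about 7
- nephrectomy: 30 × 55/141 = 11.7, about 12
- prostatectomy: 30 × 55/141 = 11.7, about 12

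**Step 3: one event at the first review.**

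| Procedure | Threshold | One Grade IV event | One death, Grade V only | One death, if V counted |
|---|---|---|---|---|
| Cystectomy | 10% | 1/7 = 14.3% | 0/7 = 0% | 14.3% |
| Nephrectomy | 8% | 1/12 = 8.3% | 0/12 = 0% | 8.3% |
| Prostatectomy | 5% | 1/12 = 8.3% | 0/12 = 0% | 8.3% |

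**Step 4: dependence on the mix.** One event exceeds threshold t only if 1/n > t. That requires n ≤ 9 for cystectomy (1/10 = 10% is not above 10%), n ≤ 12 for nephrectomy (1/13 = 7.7%), and n ≤ 19 for prostatectomy (1/20 = 5% is not above 5%). If the first 30 were a random draw from 31/55/55, these limits would hold in 92%, 63% and over 99% of draws singly, and all together in 56%. The draw may not be random: the 15 roll-in cases come from two sites (Section 6.1), and Section 6.4.2 expects few cystectomies, which would raise the other two counts.

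For larger cohorts more events are needed. The smallest count above the threshold is floor(t × n) + 1:

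| Subjects of one procedure | Cystectomy | Nephrectomy | Prostatectomy |
|---|---|---|---|
| 10 | 2 | 1 | 1 |
| 20 | 3 | 2 | 2 |
| 30 | 4 | 3 | 2 |

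So the number of events that matters changes with the mix. The zero weight given to a death-only record does not.

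**Step 5: added crossings if deaths are counted.** The chance of at least one death among the first 30 is 1 − (1 − p)^30. The documents give no expected 30-day death rate for this trial, so p is assumed: 0.2% gives 5.8%, 0.5% gives 14.0%, 1% gives 26.0%. Each is an upper bound on the extra crossings at that review, since not every death would tip a rate over its limit.

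**The case against.** The strongest reply is that deaths are already watched more closely than Grade IV events. They are reported as soon as possible, every one goes to the CEC, device-associated events that endanger subjects are a listed reason to suspend, and the list is open. Crossing a Grade IV threshold does not halt the trial automatically either; the sponsor decides whether to modify or stop. All of this stands. A reader might infer that deaths go unreviewed or cannot stop the trial, and the documents do not support that. What is missing is a numeric trigger: CEC review of a death settles relatedness, and the open list leaves action to judgment.

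It could also be said that the 30-day mortality goals in Section 14.5 supply a number. For nephrectomy the text reads "A value of 0.243 provides 10% margin on the upper limit, while remaining clinically appropriate". That section treats the secondary goals as aids to interpretation, so they are not stopping limits.

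A further reply is that any sponsor would count deaths in practice. That may be so, but leaving one out would comply with the text.

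Two cautions on the size also stand. The first-review percentages depend on the mix, most of all for nephrectomy, where 13 subjects instead of 12 reverses the result. It is also tempting to argue that at the second review one Grade IV event plus one death would stay under every limit. That needs a cumulative count of 60, whereas the protocol speaks of the second 30 subjects, so I do not rely on it.

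**Conclusion.** The point holds as a gap in a stated safety rule. On the literal text of Section 16.10.2.1, a complication recorded only as Grade V adds zero to the rates the sponsor is to act on, and no other numeric trigger in the available text includes deaths. That conclusion needs no assumption about the mix.

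The illustration, in which one Grade IV event reads above every threshold and one death reads 0%, is conditional on about 7, 12 and 12 subjects in the first 30 and on the pooled reading of that 30.

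The conclusion does not extend to oversight of deaths in general, nor to fatal courses in which an earlier Grade IV event was reported separately. Section 6.5 (Study Oversight) and the CEC charter were not available, so a wider rule there cannot be excluded; Section 16.10.2.1 does not refer to one.

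**What to change.** In Section 16.10.2.1, replace Grade IV with *Grade IV or V (including death)* in the continuous-monitoring, threshold and review sentences. Keep the levels at 10%, 8% and 5%.

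Add one sentence: *A subject who dies within 30 days of the procedure is counted as having 30-day data, in both the numerator and the denominator.* Without it, a subject who dies before the 30-day visit could be taken as lacking 30-day data and drop out of the rate.

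Do not make the second review cumulative by default. With 12 nephrectomy subjects in the second 30, one event reads 8.3%. Over 60 subjects the planned mix gives 60 × 55/141 = 23.4, and 1/23 = 4.3%, so pooling would make the rule less sensitive.

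No new data are needed, because deaths are already reported and adjudicated. The cost is a protocol amendment, which under Section 16.6 needs FDA and IRB approval before use, and a somewhat higher chance of crossing a threshold, bounded at the first review by the figures in Step 5. Since the response is to modify or stop, a crossing still leaves the sponsor room for a proportionate decision.

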16.10.2.2 Investigator/Study Site Termination or Suspension

Possible reasons for an Investigator or study site termination or suspension include but are not limited to:

- Failure to obtain initial IRB approval or annual renewal of the study

- Persistent non-compliance to the clinical investigation (e.g. failure to adhere to inclusion/exclusion criteria, failure to follow subjects per scheduled follow-ups)
- Lack of enrollment
- Noncompliance to regulations and the terms of the CTA (e.g. failure to submit data in a timely manner, failure to follow-up on data queries and monitoring observations in a timely manner, etc.)
- IRB suspension of the study site
- Fraud or fraudulent misconduct is discovered (as defined by local law and regulations)
- Investigator request (e.g., no longer able to support the study)

16.10.3 Procedures for Termination or Suspension

16.10.3.1 Medtronic-initiated and Regulatory Authority-initiated

- Medtronic will promptly inform the clinical Investigators of the termination or suspension and the reasons and inform the RAs where required
- In the case of study termination or suspension for reasons other than a temporary IRB approval lapse, the Investigator will promptly inform the IRB
- In the case of study termination, the Investigator must inform the subjects and may inform the personal physician of the subjects to ensure appropriate care and follow-up is provided
- In the case of a study suspension, subject enrollment must stop until the suspension is lifted by Medtronic
- In the case of a study suspension, enrolled subjects should continue to be followed out of consideration of their safety, rights and welfare

16.10.4 Procedures for Termination or Suspension

16.10.4.1 Investigator-initiated

- The Investigator will inform Medtronic and provide a detailed written explanation of the termination or suspension
- The Investigator will promptly inform the institution (where required per regulatory requirements)

- The Investigator will promptly inform the IRB
- The Investigator will promptly inform the subjects and/or the personal physician of the subjects to ensure appropriate care and follow-up is provided
- In the case of a study suspension, subjects enrolled should continue to be followed out of consideration of their safety, rights and welfare

18.1 RAS URO Clavien-Dindo Grades and Examples

Reference: Dindo D, Demartines N, Clavien PA. Classification of surgical complications: a new proposal with evaluation in a cohort of 6336 subjects and results of a survey. *Ann Surg*. 2004;240(2):205-213.

<https://www.ncbi.nlm.nih.gov/pubmed/15273542>

Grade	Definition
Grade I	Any deviation from the normal postoperative course without the need for pharmacological treatment or surgical, endoscopic, and radiological interventions. Allowed therapeutic regimens are: drugs as antiemetics, antipyretics, analgetics, diuretics, electrolytes, and physiotherapy. This grade also includes wound infections opened at the bedside.
Grade II	Requiring pharmacological treatment with drugs other than such allowed for grade I complications. Blood transfusions and total parenteral nutrition are also included.
Grade III	Requiring surgical, endoscopic or radiological intervention
Grade IIIa	Intervention not under general anesthesia
Grade IIIb	Intervention under general anesthesia
Grade IV	Life-threatening complication (including CNS complications)* requiring IC/ICU management

Medtronic Expand URO Clinical Investigation Plan

MDT19051EINURO

Version 9.0

Page 106 of 111

Medtronic

Grade	Definition
Grade IVa	Single organ dysfunction (including dialysis)
Grade IVb	Multiorgan dysfunction
Grade V	Death of a patient

*Brain hemorrhage, ischemic stroke, subarachnoidal bleeding, but excluding transient ischemic attacks. CNS, central nervous system; IC, intermediate care; ICU, intensive care unit.

Grades	Organ System	Examples
Grade I	Cardiac	Atrial fibrillation converting after correction of K ⁺ -level
	Respiratory	Atelectasis requiring physiotherapy
	Neurological	Transient confusion not requiring therapy
	Gastrointestinal	Noninfectious diarrhea

Grades	Organ System	Examples
	Renal	Transient elevation of serum creatinine
	Other	Wound infection treated by opening of the wound at the bedside
Grade II	Cardiac	Tachyarrhythmia requiring β -receptor antagonists for heart rate control
	Respiratory	Pneumonia treated with antibiotics on the ward
	Neurological	TIA requiring treatment with anticoagulants
	Gastrointestinal	Infectious diarrhea requiring antibiotics
	Renal	Urinary tract infection requiring antibiotics
	Other	Same as for I but followed by treatment with antibiotics because of additional phlegmonous infection
Grade IIIa	Cardiac	Bradyarrhythmia requiring pacemaker implantation in local anesthesia

Medtronic Business Restricted

This document is electronically controlled

CONFIDENTIAL 056-F275 Rev E Clinical Investigation Plan Template

Medtronic Expand URO Clinical Investigation Plan

MDT19051EINRUO

Version 9.0

Page 107 of 111

Medtronic

Grades	Organ System	Examples
	Neurological	See grade IV
	Gastrointestinal	Biloma after liver resection requiring percutaneous drainage
	Renal	Stenosis of the ureter after kidney transplantation treated by stenting
	Other	Closure of dehiscent noninfected wound in the OR under local anesthesia
Grade IIIb	Cardiac	Cardiac tamponade after thoracic surgery requiring fenestration
	Respiratory	Bronchopleural fistulas after thoracic surgery requiring surgical closure
	Neurological	See grade IV
	Gastrointestinal	Anastomotic leakage after descendorectostomy requiring relaparotomy
	Renal	Stenosis of the ureter after kidney transplantation treated by surgery
	Other	Wound infection leading to eventration of small bowel
Grade IVa	Cardiac	Heart failure leading to low-output syndrome
	Respiratory	Lung failure requiring intubation
	Neurological	Ischemic stroke/brain hemorrhage
	Gastrointestinal	Necrotizing pancreatitis
	Renal	Renal insufficiency requiring dialysis
Grade IVb	Cardiac	Same as for IVa but in combination with renal failure
	Respiratory	Same as for IVa but in combination with renal failure
	Gastrointestinal	Same as for IVa but in combination with hemodynamic instability
	Neurological	Ischemic stroke/brain hemorrhage with respiratory failure
	Renal	Same as for IVa but in combination with hemodynamic instability
Suffix "d"	Cardiac	Cardiac insufficiency after myocardial infarction (IVa-d)
	Respiratory	Dyspnea after pneumonectomy for severe bleeding after chest tube placement (IIIb-d)

Medtronic Business Restricted

This document is electronically controlled

CONFIDENTIAL 056-F275 Rev E Clinical Investigation Plan Template

Grades	Organ System	Examples
	Gastrointestinal	Residual fecal incontinence after abscess following descendorectostomy with surgical evacuation. (IIIb-d)
	Neurological	Stroke with sensorimotor hemisynrome (IVa-d)
	Renal	Residual renal insufficiency after sepsis with multiorgan dysfunction (IVb-d)
	Other	Hoarseness after thyroid surgery (I-d)

TIA, transient ischemic attack; OR, operating room.

